#### **4.5.1.2 Evaluation in the anti-VEGF Incomplete Responder Population C**

For the evaluation of efficacy in the anti-VEGF–incomplete-responder all patients in the population C will be used.

The primary efficacy variable is BCVA change from Week 12 to Week 36. The primary efficacy analysis will be performed using a MMRM model described in section 4.5.1.1.

The model-based estimate of the difference in change from baseline between the treatment group (Arm E) and the control group (Arm A) means at Week 36, together with 95% Confidence and corresponding p-value will be reported as the primary efficacy measure in this population.

The mean and 95% confidence intervals within each treatment group and for the difference between RO6867461 treatment group and the control group change from baseline at the other time points will also be reported. There will be no formal correction for multiple comparisons.

#### **4.5.2 Secondary Efficacy Endpoints**

All analyses of secondary efficacy endpoints as defined in section 2.2.2 will be performed for population A and for population C, using their respective baseline definition (see 4.4.2).

For all secondary endpoints measured on a continuous scale, the same MMRM model used for the change from baseline BCVA will be employed. Nominal p-values for treatment effect will be reported for all post-baseline visits without correction for multiple testing.

Binary endpoints will be analyzed using Generalized Estimating Equations (GEE) with a binomial distribution, logit link function for odds ratios and identity link for risk differences, and unstructured covariance. In case of convergence issues, other covariance structures, such as AR(1) covariance structure, will be used.

The model will include the categorical covariates of treatment group, visit, and visit by treatment group interaction and randomization stratification indicator for presence of RAP or PCV and the continuous covariate of baseline outcome measure.

Least squares means on the probability scale for each treatment arm with the corresponding 95% confidence intervals and odds ratios relative to the control arm will be computed for all post-baseline visits.

Data transformation (e.g., logarithmic transformation) may be applied as appropriate. Other statistical models and additional analyses may also be performed as appropriate. Fisher's exact test may be used for binary endpoints in case GEE models do not converge.

In addition, the influence of baseline parameters will be evaluated as covariates in the MMRM model and in subgroup analysis as appropriate (see Section 4.5.5 ).

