6.6.1.2 Evaluation in the Anti-VEGF–Incomplete-Responder Population

For the evaluation of efficacy in anti-VEGF–incomplete-responder population, Population B and a subgroup of Population B will be used.

The subgroup is defined as:

- Patients with BCVA ≤ 68 Letters at Week 12

The study Week 12 visit will be considered the baseline for all efficacy evaluations for the anti-VEGF–incomplete-responder population.

The primary efficacy variable is BCVA change from Week 12 to Week 36. The primary efficacy analysis will be performed using a MMRM model. The model will include the categorical covariates of treatment group, visit, and visit by treatment group interaction, and the continuous covariate of Week 12 BCVA. Other covariates including the categorical stratification factors of baseline BCVA (≥ 69 letters vs. ≤ 68 letters) and

presence of RAP or PCV may also be incorporated as appropriate. An unstructured covariance structure will be used to account for within patient correlation, but another variance-covariance structure may be selected in case of convergence issues.

The primary statistical test will aim to test the null hypothesis (H_0) of no difference between the treatment group (Arm E) and the control group (Arm A), in terms of BCVA mean change from Week 12 to Week 36. The model-based estimate of the difference between the treatment group (Arm E) and the control group (Arm A) at Week 36, together with 95% Confidence and corresponding p-value will be reported as the primary efficacy measure in this population.

The mean and 95% CI within each treatment group and for the difference between RO6867461 treatment group and the control group at the other time-points will also be reported. There will be no formal correction for multiple testing.

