#### **4.4.2 Baseline**

For the evaluation in the treatment-naïve population, the baseline measurement is the latest non-missing observation before the first dose of study medication. For the evaluation in the anti-VEGF–incomplete-responder population, the baseline is the observation from Study Week 12. If the week 12 observation is missing, the patient will not be included in the incomplete responder population. For patients who did not receive any study medication, baseline will be set as the last available assessment before and including day 1.

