#### **4.5.1 Primary Efficacy Endpoint**

##### **4.5.1.1 Evaluation in the Treatment-Naïve Population**

For the evaluation of efficacy in the treatment-naïve population, all patients in Population A will be used.

The primary efficacy variable is the BCVA change from baseline to Week 36. The primary efficacy analysis will be performed using a Mixed Model for Repeated Measurement (MMRM) model. The model will include the categorical covariates of randomization stratification indicator for presence of RAP or PCV, treatment group, visit, and visit by treatment group interaction and the continuous covariate of baseline BCVA. An unstructured variance-covariance model will be used to account for within-patient correlation, but another variance-covariance structure, such as AR(1), may be used in case of convergence issues.

In case of a significant departure from the normality assumptions required for the MMRM, a nonparametric Mann-Whitney  $U$  test will be used to compare change from baseline between treatment arms at given visits.

The primary statistical tests will test the null hypotheses:

$H_0$ : no difference between each of the treatment group (Arms B, C, or D) and the control group (Arm A), in mean BCVA change from baseline to Week 36 vs.

$H_A$ : Arms B, C or D means are different from Arm A mean.

The model-based estimate of the difference between each of the treatment group (Arms B, C, and D) and the control group (Arm A) at Week 36, together with 95% confidence intervals and corresponding p-value will be reported as the primary efficacy measures in this population.

The mean and 95% confidence interval (CI) within each treatment group and for the difference in change from baseline between RO6867461 treatment groups (Arms B, C, and D) and the control group (Arm A) at the other time-points will also be reported. There will be no formal correction for multiple comparisons.

For the primary endpoints, a statistically significant difference at week 36 between any of the treatment Arms B, C, or D and Arm A will be concluded if the corresponding unadjusted 2-sided p-value is below 0.2.

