#### **4.5.4 Sensitivity Analyses**

Effects of prognostic factors on the BCVA change from baseline will be investigated using the MMRM model described in section 4.5.1. The measurement at BL (baseline) of each of the following variables may be used as covariates in the model:

- Age
- CNV component area, (FFAArea)
- LLD (Difference between BCVATOT for the BCVA assessment and LLVATOT for the LLVA assessment)

The sensitivity analyses will be performed separately for each covariate in populations A and C.

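### SAP 4.5.2 does not state own-baseline adjustment for the continuous anatomical endpoints; read literally, baseline BCVA is their only continuous covariate (low severity, cheap precision gain)

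*SAP*

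**What the plan says.** SAP 2.2.2 lists five continuous anatomical secondary endpoints: change in foveal center point thickness and CST by SD-OCT, and change in CNV area, CNV component area and leakage area by FFA. For these, SAP 4.5.2 says that "the same MMRM model used for the change from baseline BCVA will be employed", and Protocol 6.6.2 uses the same cross-reference.

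The model referred to is in SAP 4.5.1.1. It has the RAP/PCV stratum, treatment, visit, "visit by treatment group interaction and the continuous covariate of baseline BCVA". No other continuous covariate is named.

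Later in SAP 4.5.2, after the GEE for binary endpoints is introduced, the model is said to include "the continuous covariate of baseline outcome measure". The next paragraph describes least squares means on the probability scale. The section ends by saying that "the influence of baseline parameters will be evaluated as covariates in the MMRM model and in subgroup analysis as appropriate", and points to the subgroup section, 4.5.5.

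**The concern.** When the outcome is a change from baseline, its own baseline is usually a strong predictor, because the baseline value enters the change with a minus sign. Adjusting for it removes that variation. Baseline BCVA is a different measurement and can stand in for baseline retinal thickness or leakage area only as far as the two are correlated.

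Followed to the letter, the SAP gives the imaging endpoints BCVA and nothing of their own. Two careful programmers could also fit different models from the same text. These endpoints are the trial's imaging evidence on mechanism of action, so the covariate should be fixed before unmasking.

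**Working it through.** **Does any passage supply the missing term?**

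- SAP 4.5.1.2, for Population C: "The primary efficacy analysis will be performed using a MMRM model described in section 4.5.1.1". Protocol 6.6.1.2 gives that population's model visit-by-treatment terms "and the continuous covariate of Week 12 BCVA". The visit moves; the variable is still BCVA.
- SAP 4.4.2: for the incomplete-responder evaluation "the baseline is the observation from Study Week 12". This fixes the time point and names no covariate.
- SAP 4.5.4: "Effects of prognostic factors on the BCVA change from baseline will be investigated using the MMRM model described in section 4.5.1". This concerns BCVA change only.
- The phrase "the continuous covariate of baseline outcome measure" stands between the GEE specification and probability-scale output, which favours reading it as part of the GEE.

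None states own-baseline adjustment for the continuous anatomical endpoints.

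**The plan's own figures.** The documents give no power, SD or correlation for these endpoints. Their nearest figure is the primary power. With 68 × 0.9 = 61.2 and 45 × 0.9 = 40.5 patients, SE = 13.5 × √(1/61.2 + 1/40.5) = 2.735. Power at 5.9 letters is Φ(5.9/2.735 − 1.2816) = 0.81, and the minimum detectable difference is 1.2816 × 2.735 = 3.5. Both match SAP 2.3.1, but they say nothing about imaging. Every input below is therefore an assumption.

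**Gain with a slope specific to Week 36.** Let k = follow-up SD / baseline SD, ρ = correlation of baseline with follow-up, r = correlation of baseline BCVA with the change, and q = correlation of baseline BCVA with own baseline.

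- Correlation of own baseline with the change: c = (ρk − 1)/√(1 + k² − 2ρk).
- Variance ratio, own baseline added against BCVA only: 1 − p², where p = (c − rq)/√((1 − r²)(1 − q²)).
- Example with k = 1, ρ = 0.5, r = q = 0: c = −0.5, ratio 0.75.

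Over r from 0 to 0.2 and q from 0 to −0.4:

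- k = 1, ρ 0.1 to 0.7: 0.46 to 0.88; extended to ρ = 0.9: up to 0.97
- k = 0.7, ρ 0.1 to 0.9: 0.24 to 0.51
- k = 1.2, same ρ: 0.58 to 1.00
- k = 1.3, same ρ: 0.63 to 1.00

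**Why the slope must vary by visit.** Protocol Appendix 1 schedules SD-OCT at 11 post-baseline visits in Population A: Weeks 1 (Day 7), 4, 8, 12, 13, 16, 20, 24, 28, 32 and 36. A single main-effect term forces one slope on all of them. Take baseline SD 1, complete data, unstructured covariance and BCVA unrelated to the endpoint. The slope of the change at visit t on own baseline is b_t = kρ_t − 1. Let S be the covariance of the changes given baseline, so that S₃₆ = k²(1 − ρ₃₆²). The fitted common slope tends to β = (1ᵀS⁻¹b)/(1ᵀS⁻¹1). The Week 36 variance is then proportional to:

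- no own baseline: S₃₆ + b₃₆²
- visit-specific slope: S₃₆
- common slope: S₃₆ + (b₃₆ − β)²

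| Assumed correlation over time | k | ρ₃₆ | S₃₆ | b₃₆ | β | Ratio, visit-specific | Ratio, common |
|---|---|---|---|---|---|---|---|
| 0.97 per week, 10% measurement noise | 1 | 0.301 | 0.910 | −0.699 | −0.239 | 0.910/1.399 = 0.65 | (0.910 + 0.212)/1.399 = 0.80 |
| 0.98 per week, no noise | 1 | 0.483 | 0.767 | −0.517 | −0.034 | 0.767/1.034 = 0.74 | (0.767 + 0.234)/1.034 = 0.97 |
| 0.98 per week, no noise | 1.2 | 0.483 | 1.104 | −0.420 | 0.160 | 1.104/1.280 = 0.86 | (1.104 + 0.336)/1.280 = 1.12 |

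The early visits, which sit closest to baseline, dominate β and pull it away from the Week 36 slope. For FFA in Population C the question does not arise, because Week 36 is the only scheduled post-baseline visit.

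**Validity and cost.** In single-visit simulations under the null (20,000 trials per setting; 61 vs 41, 40 vs 40 and 31 vs 31 patients), mean estimates were within 0.004 SD of zero and type I error was 0.191 to 0.206 at nominal 0.20. At a no-gain point (k = 1.2, ρ = 0.8, BCVA unrelated), adding one term gave variance ratios of 1.009 to 1.013, a cost of about 1%. The finite-sample cost of the visit interaction was not simulated.

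**The case against.** The strongest reply is that the authors meant the same model form with the covariate following the outcome. In the BCVA model, baseline BCVA is the outcome's own baseline, so carrying that role over to CST is natural. The SAP already reuses 4.5.1.1 for Population C without restating the covariate. The phrase "the continuous covariate of baseline outcome measure" also fits a pure GEE reading imperfectly. Entry requires fluid on SD-OCT (Protocol 4.2.1), so the Population A baseline of the no-fluid endpoint is binary and nearly constant, and cannot serve as a continuous covariate. This is plausible and may be what was intended. But for the three binary BCVA endpoints a continuous baseline does exist, so the phrase still makes sense within the GEE, and no sentence says that the covariate changes with the endpoint.

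SAP 4.5.2 also permits other models and evaluates baseline parameters as covariates, and SAP 4.5 refers to a list of planned outputs that is not among the documents. Those are additional analyses; they do not define the main model.

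A reader might infer that the imaging comparisons are biased or their p-values invalid. The documents do not support that. Treatment is randomised, and in Population C both arms receive only ranibizumab until the Week 12 assessments are done. Nor is chance baseline imbalance a second harm on top of lost precision. With k = 1 and ρ = 0.5 the slope on baseline is −0.5; its square, 0.25, is exactly the share of variance that adjustment removes (1 − 0.75). The standard error already includes it.

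**Conclusion.** The point stands as a low-severity improvement. Read literally, the text leaves five continuous secondary endpoints without their own baseline; own-baseline adjustment is possibly intended but not stated. What is at stake is precision on endpoints reported with nominal p-values, in a study that SAP 4.8 calls hypothesis-generating.

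The gain runs from large to none, depending on SDs and correlations that the documents do not give. With a visit-specific slope the large-sample Week 36 variance does not rise. That statement assumes complete data and a BCVA term that fits Week 36 equally well with and without own baseline. A reader might infer that adding own baseline in any form is harmless; the third scenario above, where a common slope gives 1.12, shows that it is not.

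**What to change.** Add to SAP 4.5.2: each continuous secondary endpoint uses the 4.5.1.1 MMRM with the baseline value of that endpoint, on the scale analysed, and its interaction with visit, added alongside baseline BCVA. Own baseline is the last pre-dose value in Population A (the screening value for FFA areas) and the Week 12 pre-treatment value in Population C.

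Add the term; do not swap it for BCVA. Day 1 BCVA is a stratification factor (SAP 3.1) and is not otherwise in the Population A model. In the single-visit case, replacing BCVA can raise the variance by up to 1/(1 − r²), which is 1.04 at r = 0.2 and 1.19 at r = 0.4. In Population C the retained covariate is Week 12 BCVA, which is not the stratification factor, so only the second reason applies there.

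If the baseline-outcome wording in 4.5.2 was meant to cover the MMRM too, saying so resolves the ambiguity; the visit interaction should still be specified.

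The cost is one or two sentences and a few model terms per endpoint. No new data are needed: SD-OCT is scheduled at screening, Day 1 and Week 12, and FFA at screening and Week 12. Footnote a of Protocol Appendix 1 places the Week 12 images before that visit's treatment, so they precede Arm E's first RO6867461 dose and are valid covariates.

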4.2.1 Inclusion Criteria

Patients must meet the following criteria at study entry.

Ocular Criteria for Study Eye:

- Treatment-naive with CNV secondary to AMD, with subfoveal CNV or juxtafoveal CNV with a subfoveal component related to the CNV activity by FFA or SD-OCT (as evidenced by subretinal fluid, subretinal hyper-reflective material, evidence of leakage, or hemorrhage)
- BCVA letter score of 73 to 24 letters (inclusive) on ETDRS-like charts (20/40 to 20/320 Snellen equivalent) on Day 1. Proportion of patients with BCVA letter score of 73 to 69 letters inclusive (20/40 Snellen equivalent) on Day 1 will be limited to a maximum of 40% of the planned sample size
- CNV lesion of all types (predominantly classic, minimally classic, or occult) with:
 - Total lesion size (including blood, atrophy, fibrosis, and neovascularization) of ≤ 6 disc areas (DAs) by FFA
 - CNV component area of $\geq 50\%$ of total lesion size by FFA
 - Active CNV confirmed by FFA (evidence of leakage)
 - CNV exudation confirmed by SD-OCT (presence of fluid)
- Clear ocular media and adequate pupillary dilatation to allow acquisition of good quality retinal images to confirm diagnosis

General Criteria:

- Able and willing to provide written informed consent and to comply with the study protocol according to International Conference on Harmonization (ICH) and local regulations. Alternatively, a legally authorized representative must be able to consent for the patient according to the ICH and local regulations
- Age ≥ 50 years

- For women who are not postmenopausal (i.e., ≥ 12 months of non-therapy-induced amenorrhea or surgically sterile (absence of ovaries and/or uterus) agreement to remain abstinent or use combined contraceptive methods that result in a failure rate of $< 1\%$ per year during the treatment period and at least through Week 36.

Examples of contraceptive methods with an expected failure rate of $< 1\%$ per year include male sterilization, hormonal implants, proper use of combined oral or injected hormonal contraceptives, and certain intrauterine devices.

Alternatively, two methods (e.g., two barrier methods such as a condom and a cervical cap) may be combined to achieve a failure rate of $< 1\%$ per year, barrier methods must always be supplemented with the use of a spermicide.

- Males must agree to use a barrier method of contraception starting from first treatment administration for at least 2 months post-last treatment administration

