#### **4.7 MISSING DATA**

An analysis of the sensitivity of the assumptions on missing values may be performed for the primary efficacy variable.

The primary endpoint analysis using the MMRM assumes a missing at random (MAR) missing-data mechanism (i.e., the probability that missing data are dependent on other observed variables, but not on the missing data itself.)

A LOCF imputation will be applied to the primary end-point as a sensitivity analysis.

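### The SAP's GEE for binary endpoints has a weaker missing-data footing than the primary MMRM, an identity link that often fails to fit, and no usable baseline covariate for dry retina in Population A

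*SAP*

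**What the plan says.** SAP 4.5.2 replaces the protocol's method for binary endpoints (Protocol 6.6.2, Fisher's exact test) with a longitudinal model: "Binary endpoints will be analyzed using Generalized Estimating Equations (GEE) with a binomial distribution", with "logit link function for odds ratios and identity link for risk differences, and unstructured covariance". Its covariates are treatment, visit, their interaction, the RAP/PCV stratum and "the continuous covariate of baseline outcome measure". The SAP does not say which variable that last term is for each endpoint.

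There are two fallbacks. The first is "In case of convergence issues, other covariance structures, such as AR(1) covariance structure, will be used". The second is that Fisher's "exact test may be used for binary endpoints in case GEE models do not converge".

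On missing data, SAP 4.7 says only that "The primary endpoint analysis using the MMRM assumes a missing at random (MAR) missing-data mechanism" and that "A LOCF imputation will be applied to the primary end-point as a sensitivity analysis". Neither sentence covers the binary endpoints.

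One of those endpoints is a dry retina on SD-OCT at Week 36 (SAP 2.2.2). Protocol 4.2.1 requires at entry "CNV exudation confirmed by SD-OCT (presence of fluid".

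**The concern.** There are three linked weaknesses.

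- **Missing data.** Standard GEE is generally guaranteed only when drop-out is completely at random or depends on covariates in the model. If drop-out depends on post-baseline vision, the MMRM can still be valid under missing at random, but unweighted GEE need not be. Such drop-out is plausible, since Protocol 4.7.1 lists worsening disease among the reasons for discontinuation. The same patients' letter scores would then support the mean-change result under a weaker assumption than the responder rates need.
- **Fitting.** A linear probability model with a continuous covariate can produce fitted values below 0 or above 1, where the binomial variance is undefined. A different working correlation does not remove that problem. If the risk-difference model fails, what remains is an optional unadjusted test that gives a p-value and no risk difference.
- **Covariate.** For dry retina in Population A, every patient should have fluid at baseline, so baseline status does not vary and cannot serve as a covariate.

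At stake are the precision, and to a lesser degree the accuracy, of the responder and dry-retina results.

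**Working it through.** **1. The plan's own figure.** The documents give no rate or power for a binary endpoint, so the primary calculation (SAP 2.3.1) anchors sample size, SD and drop-out. Completers are 0.9 × 68 = 61.2 and 0.9 × 45 = 40.5. The SE is 13.5 × √(1/61.2 + 1/40.5) = 2.73 letters. The minimum detectable difference is 1.2816 × 2.73 = 3.50 letters. Power for 5.9 letters at one-sided 10% is 0.809. Both agree with the SAP (3.5 letters, approximately 80%).

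**2. Arithmetic bound for observed cases.** With drop-out fraction d, the bias in one arm is d × (completer response rate − drop-out response rate). At d = 0.10 and a gap of 10 to 40 points, this is 1 to 4 points.

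**3. Simulated bias for a gain of at least 15 letters.** From the SAP: SD 13.5, effect 5.9 letters, 10% average drop-out. From Protocol Appendix 1: nine post-baseline BCVA visits. Assumed, because the documents are silent: control gain about 8 letters, between-visit correlation about 0.75 to 0.9, baseline–change correlation −0.3, and drop-out log-odds changing by 0.08 per letter of the last observed change. Observed-case rows use 100,000 patients per arm. GEE rows average four runs of 6,000 per arm, with baseline BCVA as covariate. Entries are bias in percentage points (control, test, difference).

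| Drop-out pattern | Observed cases | Unstructured GEE |
|---|---|---|
| 10% in each arm, poor responders leave | +2.29, +2.98, +0.70 | +0.77, +0.89, +0.13 |
| 15% control, 5% test | +3.54, +1.52, −2.03 | +0.81, +0.45, −0.37 |
| 10% in each arm, opposite mechanisms | +2.25, −3.11, −5.36 | +0.78, −0.67, −1.46 |

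The Monte Carlo SE of the GEE differences is about 0.1. In the first pattern an independence working structure gave about +2.0 and +2.5 per arm, so the protection comes from the working correlation. In a single run at 20% drop-out in both arms, unstructured GEE was off by 31.87 − 30.65 = +1.2 and 49.89 − 47.78 = +2.1.

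For scale, with response rates of 32% and 48% in 61 and 41 completers, the SE of the risk difference is √(0.32 × 0.68/61 + 0.48 × 0.52/41) = 9.8 points. The worst GEE bias is 1.46/9.8 = 0.15 SE, and the worst observed-case bias is 5.36/9.8 = 0.55 SE.

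**4. Convergence, same endpoint, assumed trajectories and drop-out.** Population C was taken as 0.65 × 68 ≈ 44 per arm. SAP 4.1.1.3 also requires a gain of at least one letter, so the true number may be smaller.

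| Model | Arm A vs one test arm (68 vs 45), failures | Population C (44 vs 44), failures |
|---|---|---|
| Identity link, unstructured | 46 of 100 | 73 of 100 |
| Identity link, AR(1) | 16 of 40 | 24 of 40 |

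The logit link with unstructured covariance failed in 2 of 200 fits. A second, separate simulation gave the same picture. The identity link failed in about half of trials under unstructured, exchangeable and independence structures, and the logit link converged every time.

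**5. Baseline covariate.** If the term means the endpoint's own yes/no status at baseline, the design matrix loses rank (3 of 4) for the 15-letter gain in both populations and for dry retina in Population A. The same applies to 20/40 or better in Population C, where every patient has 68 letters or fewer. Status does vary for 20/40 and 20/200 in Population A. If it means the baseline letter score, the BCVA endpoints have no problem. For dry retina no continuous variable is named on either reading.

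**6. Remedies under the step 3 drop-out.** For 10% in each arm, the full-data rates were 31.4% and 48.1%. Inverse-probability weighting gave 31.4% and 48.1%, and imputing letters before dichotomising gave 31.4% and 48.2%. Across all three patterns the difference stayed within about 0.1 point of full data. Both remedies suited the way the data were generated, so good recovery is expected.

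**The case against.** The case for leaving the plan alone has real force.

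- **Size.** The planned analysis is unstructured GEE, not observed cases, and its simulated bias is about 0.01 to 0.15 SE. A reader might infer that the responder and mean-BCVA results could disagree because of the missing-data method alone. The planned model does not support that.
- **Validity.** A reader might infer that GEE is valid only if drop-out is unrelated to vision. Drop-out that depends on modelled covariates, including baseline BCVA if that is the covariate, is allowed. Only dependence on post-baseline outcomes is a difficulty.
- **Covariate.** A reader might infer that the covariate is constant for most endpoints. The SAP calls it continuous, which for BCVA endpoints most naturally means the letter score. In Population C that score is capped at 68 but varies. Week 12 dry-retina status should vary there too, since SAP 4.1.1.3 defines a subgroup by it. A constant term would drop out and cost precision, without in itself biasing a randomised comparison. For the 15-letter gain, omitting baseline BCVA costs about 0%, 5% or 17% efficiency at assumed baseline–change correlations of −0.1, −0.3 or −0.5.
- **Convergence.** A single Population A model would estimate the working correlation from 68 + 3 × 45 = 203 patients, and Population C has only six post-baseline BCVA visits. The two-arm fits in step 4 may not carry over exactly, and failure rates depend on software.

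Most of this stands. It does not rescue the identity link, which failed even under an independence structure, where no working correlation has to be estimated. Nor does it supply a missing-data statement for the binary endpoints or a covariate for dry retina in Population A.

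**Conclusion.** The point holds in limited form. The binary analysis lacks the missing-at-random footing stated for the primary, but under the planned unstructured GEE the consequence is small: under 1 point per arm and at most about 1.5 points in the difference at 10% average drop-out. It becomes noticeable, at about 2 to 5 points in the difference, only if the analysis falls back to observed cases and drop-out differs between arms. With the same mechanism in both arms, the observed-case difference moved by only 0.7 points.

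That fallback is a realistic prospect for risk differences, because the identity link failed in about half of simulated trials and the planned covariance alternatives did not cure it. The covariate is unspecified, and the clear gap is dry retina in Population A.

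The bias and convergence figures rest on assumed trajectories, correlations and drop-out models that are not in the documents. These are secondary endpoints with nominal p-values in a study that SAP 4.8 calls hypothesis-generating, so this is a desirable change and not an essential one.

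**What to change.** - **Risk differences.** Obtain Week 36 risk differences by standardising a logit model over the observed covariates, and drop the identity link.
- **BCVA responder endpoints.** Multiply impute the letter score under missing at random with the MMRM's terms and then dichotomise, or use drop-out-weighted GEE. Use baseline BCVA as covariate (Week 12 BCVA in Population C).
- **Dry retina.** Use weighted GEE, or impute the binary status directly, with baseline CST as covariate. SAP Table 1 defines intraretinal fluid and cysts as presence or absence, so they cannot be derived from imputed thickness.
- **Text.** State the missing-data assumption for binary endpoints, and keep the planned logit GEE as a supplement.

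The cost is extra programming only, with no new data and no change to the primary analysis. The only sensitivity method SAP 4.7 names is LOCF, so the imputation code would be new. Any drop-out model must be sparse: 10% of 203 is about 20 drop-outs in Population A, or 4 to 5 per 45-patient arm.
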